## 5. TREATMENT OF SUBJECTS

### 5.1 Investigational product/treatment

The investigational treatment is SRT delivered in five fractions. This treatment is described in more detail in paragraphs 8.3.1-8.3.9. The standard treatment of stereotactic radiotherapy delivered in one or three fractions is also described in those paragraphs.

### 5.2 Use of co-intervention (if applicable)

N/A

### 5.3 Escape medication (if applicable)

N/A

## 6. INVESTIGATIONAL PRODUCT

The study does not include use of a medicinal product, food product, medical device or other product. Therefore, this chapter is not applicable.

**7. NON-INVESTIGATIONAL PRODUCT**

No challenge agents or products used to assess endpoints are used in the trial. Therefore, this chapter is not applicable.

## 8. METHODS

### 8.1 Study parameters/endpoints

#### 8.1.1 Main study parameter/endpoint

Incidence of adverse local event (ALE) at 2 years post-radiotherapy with respect to baseline.

Definition of ALE = either radionecrosis or local failure according to Response Assessment in Neuro-Oncology Brain Metastases (RANO-BM).

Definition of radionecrosis = increasing size and low perfusion MR by interpretation of a dedicated radiologist (multidisciplinary board).

Definition of local failure is  $\geq 20\%$  increase in sum longest distance relative to nadir in target lesion.

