## 2. OBJECTIVES

Primary Objective: To determine if the percentage of adverse local events (either local failure or radionecrosis) can be reduced by using fSRT versus SRT in one or three fractions 2 years post-SRT.

Secondary Objective(s): To investigate if fSRT provides better quality of life and lower incidence of epilepsy versus SRT in one or three fractions. Additionally, to estimate overall survival as well as the cumulative incidence of local failure or radionecrosis with death as competing risk.

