#### 8.1.2 Secondary study parameters/endpoints

- Survival time/survival at 2 years post-SRT
- Incidence of symptomatic radionecrosis
- Incidence of symptomatic local failure
- Incidence of salvage treatments at 2 years post-SRT
- Distant brain recurrences at 2 years post-SRT
- Dose dexamethasone at baseline, 3 months after radiotherapy and thereafter every three months until 2 years
- Anti-epileptic drug (AED) use
- Bevacizumab use
- Grade 2 or more toxicity (CTCAE v5.0)
  - Alopecia, cognitive symptoms, fatigue, dysphasia, hearing loss, visual impairment, generalized muscle weakness

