### **8.3.9 MR imaging after SRT**

Tumor response evaluation as well as presence of distant brain recurrences are monitored every three months after SRT on contrast-enhanced (single - triple dose Gd is allowed) T1-sequences, maximum slice thickness 3 mm, field strength (1.0-3.0 Tesla with a 3D-distortion correction protocol including perfusion MR).

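### Local failure is defined without a perfusion condition, so necroses that grow by 20% or more also count as local failures and blur the tumour-control component; the primary composite is not affected.

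*Protocol*

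**What the plan says.** The primary endpoint is a composite. Protocol section 8.1.1 states: "Definition of ALE = either radionecrosis or local failure according to Response Assessment in Neuro-Oncology Brain Metastases (RANO-BM"). It then defines each part in its own words.

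- Radionecrosis: "Definition of radionecrosis = increasing size and low perfusion MR by interpretation of a dedicated radiologist (multidisciplinary board"). Low perfusion is required, but no minimum growth.
- Local failure: at least a 20% "increase in sum longest distance relative to nadir in target lesion". Minimum growth is required, but nothing is said about perfusion.

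Neither definition excludes the other, and no order of precedence is given.

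The primary objective in section 2 concerns the composite only: "To determine if the percentage of adverse local events (either local failure or radionecrosis) can be reduced by using fSRT". So do the sample size (4.4), the primary test (10.1) and the competing-risk analysis (10.2). The two parts appear separately among the secondary endpoints in section 8.1.2, as "Incidence of symptomatic radionecrosis" and "Incidence of symptomatic local failure". Section 8.3.9 specifies three-monthly follow-up MRI with a "3D-distortion correction protocol including perfusion MR", so the information needed to separate the two is collected.

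**The concern.** The two labels are meant to describe different things: treatment damage and tumour regrowth. As written, a growing necrosis carries both labels once it passes 20%. Anyone who codes local failure from section 8.1.1 will then count some necroses as tumour failures.

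This matters because the protocol expects an effect on both parts. The Summary says that earlier retrospective work found fewer necroses and also fewer recurrences with fractionation, and section 9.5 expects the arms to differ in both local control and radionecrosis. If five fractions reduces necrosis, recorded local failure falls with it even when tumour control is the same. If tumour control is somewhat worse, the fall in necrosis can conceal that. The error favours the five-fraction arm whenever the trial's hypothesis about necrosis is true.

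**Working it through.** **1. The plan's own figure.** Section 4.4 gives 30% v 10% for the composite, two-sided alpha 0.05, a pooled-variance Z test and 59 per arm, with power 0.8051 and actual alpha 0.0507. Exact binomial enumeration of that test gives power 0.8051 at 59 per arm (0.797 at 58) and an actual alpha of 0.0507 at a common rate of 10%. The stated design reproduces.

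**2. How each kind of lesion is labelled under section 8.1.1.**

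| Growth | Perfusion | Radionecrosis | Local failure | Adverse local event |
|---|---|---|---|---|
| Below 20% | Low | Yes | No | Yes |
| 20% or more | Low | Yes | **Yes** | Yes |
| 20% or more | Not low | No | Yes | Yes |
| Below 20% | Not low | No | No | No |

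Only the second row is double-labelled. It is one adverse local event either way, so step 1 does not depend on how it is labelled. The radionecrosis count does not depend on it either.

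**3. Effect on the local-failure count.** Let L be the true tumour-failure rate, R the necrosis rate, and s the share of necroses growing by 20% or more. With the two kinds of event kept separate:

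- composite = L + R
- local failure as written = L + s × R

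The protocol gives only the composite rates (30% and 10%). L, R and s are assumptions, so s is run over its whole range.

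**4. Equal tumour control.** Assume L = 5% v 5% and R = 25% v 5%, so that the composite is 30% v 10% as planned. The last column is the exact probability that a two-sided pooled Z test at 59 per arm declares a difference in local failure, when the true difference is zero.

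| s | Standard: 5 + 25s | Five fractions: 5 + 5s | Apparent difference | Chance of nominal significance |
|---|---|---|---|---|
| 0 | 5% | 5% | 0 points | 4.6% |
| 0.25 | 11.25% | 6.25% | 5 points | 16% |
| 0.5 | 17.5% | 7.5% | 10 points | 38% |
| 0.75 | 23.75% | 8.75% | 15 points | 62% |
| 1 | 30% | 10% | 20 points | 81% |

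**5. Worse tumour control.** Assume L = 5% v 8% and R = 25% v 2%, again 30% v 10% in total. Local failure as written is 5 + 25s v 8 + 2s. The direction reverses when 5 + 25s > 8 + 2s, that is, when s > 3/23, about 13%. At s = 0.5 it reads 17.5% v 9% in favour of five fractions, although true failure is 3 points worse there.

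**6. Scope.** These are rates of all local failures. The listed secondary endpoint is the symptomatic subset, for which the protocol gives no rate. The mechanism is the same, but the size in that subset cannot be calculated.

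**The case against.** The strongest reply is that nothing primary is touched, and that stands. The objective, test, sample size and competing-risk analysis all use the composite, and a lesion that meets both definitions is still one event.

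A reader might go further and infer that the trial cannot tell less necrosis from better tumour control at all. The protocol does not support that. Radionecrosis needs low perfusion and a specialist reading, so it can be counted cleanly by arm. Perfusion MR is acquired, so lesions growing by 20% or more could be split by perfusion later. What is missing is a rule, not the data. Even so, the trial is open label and no masked reading is described, so a rule chosen once outcomes are known is weaker than one fixed now.

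A reader might also infer that most necroses would be absorbed into local failure. The protocol gives no distribution of growth, so s could lie anywhere from 0 to 1. The case where every necrosis grows by 20% or more is an extreme.

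Two further replies carry some weight. Section 8.1.1 refers to RANO-BM, which might contain a separating rule. That source was not available to check, and the protocol's own wording, written out after the reference, contains none. Precedence between components could also be settled in a statistical analysis plan. But this is not a detail left open: the protocol states the definition of local failure, and followed as stated it counts necrosis.

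**Conclusion.** The concern holds for the local-failure component, and only for that. On the wording of section 8.1.1, a low-perfusion lesion growing by 20% or more from nadir is both a radionecrosis and a local failure. Local failure, and with it symptomatic local failure, is therefore not a clean measure of tumour control.

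With equal true failure of 5% and necrosis of 25% v 5%, the spurious difference in local failure runs from 0 to 20 points, with 10 points at s = 0.5. With slightly worse control under five fractions, the direction can reverse at a fairly small s. These sizes rest on assumed component rates within the planned 30% v 10%. The existence and direction of the distortion need only that some necroses grow by 20% or more and that necrosis differs between arms. The point is worth correcting because it governs how a secondary endpoint is read. It does not threaten the primary result.

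**What to change.** In section 8.1.1:

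1. Keep the radionecrosis definition as it is, with no growth threshold.
2. Add to local failure: *and not classified as radionecrosis by the multidisciplinary board*.
3. Name a default class for lesions that meet the 20% rule but have mixed, unclear or missing perfusion.
4. Report each component by arm beside the composite.

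The growth threshold should not be placed on radionecrosis as well. That would drop necroses growing by less than 20% from the primary endpoint. Under the assumptions of step 4 at s = 0.5, the composite would fall from 30% v 10% to 17.5% v 7.5% (5 + 0.5 × 25 v 5 + 0.5 × 5), and power at 59 per arm from 80.5% to 38%.

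With the wording above, every reclassified lesion remains an adverse local event, so the event count, sample size and scan schedule do not change. Confining the default class to lesions that already meet the 20% rule keeps this true. The cost is one clause, one default rule and two extra table rows. The drawback is that the default for unclear perfusion is somewhat arbitrary; showing the component results under the other choice would reveal how much it matters.

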#### 8.1.2 Secondary study parameters/endpoints

- Survival time/survival at 2 years post-SRT
- Incidence of symptomatic radionecrosis
- Incidence of symptomatic local failure
- Incidence of salvage treatments at 2 years post-SRT
- Distant brain recurrences at 2 years post-SRT
- Dose dexamethasone at baseline, 3 months after radiotherapy and thereafter every three months until 2 years
- Anti-epileptic drug (AED) use
- Bevacizumab use
- Grade 2 or more toxicity (CTCAE v5.0)
  - Alopecia, cognitive symptoms, fatigue, dysphasia, hearing loss, visual impairment, generalized muscle weakness

#### 8.1.3 Other study parameters

Facultative endpoints:

- HRQoL (measured with EORTC QLQ-C30 and QLQ-BN20) at baseline, 3, 6, 12, 18 and 24 months after radiotherapy
- IADL (measured with EQ-5D 5L) at baseline, 3, 6, 12, 18 and 24 months after radiotherapy

### 8.2 Randomization, blinding and treatment allocation

Patients who meet the inclusion criteria (see paragraph 4.2) can be included in the study after consultation with the radiation oncologist and after they have signed informed consent. They will be randomized into either of the two cohorts.

Blinding of the groups cannot be performed, because the planning system needs to calculate the treatment time based on the fractionation schedule, which is determined by randomization. The involved employees of the radiation department need to process the data in the radiation therapy software and they need to carry out QA checks on the radiation treatment plans. The latter can only be performed if all information is available.

[figure not shown]
Patients who are randomized into the standard treatment group will receive the treatment as currently advised by the LPRNO guidelines. Patients will receive 1 fraction of SRT, unless it concerns a large tumor in proximity to the brainstem or a large tumor in proximity to other metastases, see paragraph 8.3.3. Based on previous literature, local progression or survival outcome are comparable for SRT in 1 or 3 fractions.

Randomization to either SRS (1 or 3 fractions, see paragraph 8.3.3) or fSRT (5x7Gy or 5x6 Gy if in brainstem, see paragraph 8.3.3) will be 1:1, stratified by institute with block sizes 4 and 6.

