## SUMMARY

**Rationale:** Stereotactic radiotherapy is one of the most frequently chosen treatment options for brain metastases. There are an increasing number of long term survivors. Brain necrosis (e.g. radionecrosis) is the most important long term side effect of the treatment, occurring in up to 40% of patients, dependent on the size of the metastasis and delivered radiotherapy dose. Retrospective studies have shown that the incidence of radionecrosis, as well as local tumor recurrence, can be decreased with a risk difference of around 20% by administrating fractionated stereotactic radiotherapy (fSRT, e.g. five fractions) over single fraction stereotactic radiotherapy, especially in large brain metastases.

**Objective:** To determine if the incidence of adverse local events (local failure or radionecrosis) can be reduced with more than 20% using fSRT versus SRT in one or three fractions.

**Study design:** Prospective, multicenter, open label, randomized, phase II study with two cohorts.

**Study population:** Patients, 18 years and older, with one or more brain metastases from solid primary tumors diagnosed on a high resolution contrast-enhanced MRI scan referred for stereotactic radiotherapy.

**Intervention (if applicable):** One group is treated with SRT in one or three fractions. The other group is treated with fSRT in five fractions.

**Main study parameters/endpoints:** The main study parameter is the incidence of adverse local event (either local failure or radionecrosis according to RANO) at 2 years post-radiotherapy with respect to baseline.

**Nature and extent of the burden and risks associated with participation, benefit and group relatedness:** The study aims to investigate a different and potentially safer treatment method than the current standard of care. It is unlikely that the risk of adverse events will be increased in the experimental cohort compared to the standard cohort. The additional burden as a result of study participation consists of the following: between two and four additional site visits for treatment in the experimental group; a total of eighteen (facultative) questionnaires spread throughout the follow-up period.

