As clinicians, we observe an increasing number of long term survivors over several years with brain metastases. Brain necrosis or radionecrosis is a long term side effect of SRT which occurs in +/-20% of patients and the incidence may increase up to +/-40% if SRT is combined with immunotherapy. Radionecrosis may cause neurologic symptoms, such as focal neurological deficits, neurocognitive dysfunction and seizures, which require treatment with steroids, bevacizumab, or sometimes even surgery. SRT is mostly delivered with an ablative high radiotherapy dose in a single fraction. In the first millimeters close to the brain metastasis, the healthy brain tissue receives a high dose as well.

In radiotherapy literature, it is known that more fractionated radiotherapy, e.g. hypofractionated radiotherapy (fSRT), may decrease side effects. fSRT means delivering the ablative dose in multiple fractions (f.e. 5 fractions) over several days instead of delivering the ablative dose within half an hour. Recent retrospective studies showed that risk difference of local failure and radionecrosis is almost 30% in larger tumors (>2.5 cm; constituting around

50% of metastases), while the incidence is equivalent in smaller metastases. To achieve a local control of more than 90% after one year, it is important to deliver a cumulative biologically effective dose (BED) of at least 50 Gy. 35 Gy in 5 fractions results in a BED of more than 50Gy. Another potential benefit of fSRT over SRT in one or three fractions is better induction of an abscopal effect. SRT in one or three fractions results in massive tumor necrosis. fSRT may result in more regulated cell death: apoptosis, with better antigen presentation of dying tumor cells. It is hypothesized that this may subsequently result in better activation of the immune cells against the cancer and better control of micrometastases outside the irradiation field. Several studies are ongoing in which SRT is combined with immunotherapy to increase systemic tumor control and thereby improve survival.

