### 4.4 Sample size calculation

Standard cohort: Mean risk of local failure or radionecrosis 1 year = 30%

Experimental cohort: Mean risk of local failure or radionecrosis experimental arm @ 1 year = 10%

Enrollment ratio standard vs experimental cohort 1:1

Alpha = 0.05

Power=0.8

Sample size standard arm n=59

Sample size experimental arm n=59

Minimum number of patients required for the study: 118

Number of patients including additional 10% to account for missing data: 130

These number were based on the following power analysis and were calculated with PASS® software (NCSS Statistical Software):

The results are based on the exact binomial test:

Numeric results of tests based on the difference: P1 - P2

H0: P1 - P2 = 0. H1: P1 - P2 = D1 ≠ 0. Test Statistic: Z test with pooled variance.

Power	Sample size group 1 (N1)	Sample size group 2 (N2)	Prop H1 Group 1 (P1)	Prop Group 2 (P2)	Diff if H0 (D0)	Diff if H1 (D1)	Target alpha	Actual alpha	Beta
0.8051	59	59	0.3000	0.1000	0.000	0.200	0.0500	0.0507	0.1949

Note: exact results based on the binomial were only calculated when both N1 and N2 were less than 100.

The total number of patients with brain metastases treated at the department of radiotherapy in our hospital in 2019 was around 150, of whom an estimated 135 would have been eligible for inclusion. Therefore, a 3-year period (as mentioned in paragraph 3) should be sufficient to include enough patients.

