### **8.7 Premature termination of the study**

The aim of the study is to investigate a different and possibly safer treatment method than the current standard of care. The study is based on the radiotherapy concept of fractionating the treatment. When the total dose of radiation is divided into several, smaller doses over a period of several days, there are fewer toxic effects on healthy cells. Therefore, the risk of adverse events in the experimental cohort is unlikely to be greater than in the standard cohort and premature termination of the study is not likely.

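### The reasons given for not blinding cover only radiotherapy staff, and nothing in the protocol masks the follow-up MRI read that feeds the primary endpoint

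*Protocol*

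**What the plan says.** The Summary describes the trial as "Prospective, multicenter, open label, randomized, phase II study with two cohorts". Section 8.2 is the protocol's blinding section, and its position is: "Blinding of the groups cannot be performed, because the planning system needs to calculate the treatment time based on the fractionation schedule". It adds that radiation department employees must process the data in their software and run quality checks on the plans, which requires full information. It names nobody else.

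The primary endpoint (8.1.1) is the incidence of ALE at 2 years, meaning radionecrosis or local failure.
- **Radionecrosis** is "increasing size and low perfusion MR by interpretation of a dedicated radiologist (multidisciplinary board"). No amount of growth or perfusion value is set.
- **Local failure** is a 20% or greater "increase in sum longest distance relative to nadir in target lesion". No reader is named for it.

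Table 1 lists the MRI assessment of ALE under standard follow-up, and 8.3.9 sets the three-monthly schedule. Neither says who reads the scans or what the reader knows.

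On expected results, the Summary cites retrospective work in which the "incidence of radionecrosis, as well as local tumor recurrence, can be decreased with a risk difference of around 20" percent. Section 4.4 plans on 30% in the standard arm and, for fSRT, "Mean risk of local failure or radionecrosis experimental arm @ 1 year = 10" percent. Section 1 gives a "risk difference of local failure and radionecrosis is almost 30% in larger tumors", but the same sentence reports equivalent incidence in smaller metastases.

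**The concern.** The practical reasons in 8.2 are sound for the people who plan and deliver treatment. They do not carry over to a person judging a scan 3 to 24 months later, who does not need the number of fractions to measure a lesion or describe its perfusion. Yet 8.2 closes the question of blinding for the whole trial on those grounds.

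A reader who knows the arm could call borderline growth less readily in one arm than in the other. That difference would enter the primary comparison as if it were a treatment effect, and intention-to-treat analysis would not remove it. The most exposed case is growth below 20% with low perfusion. It can be an event through the radionecrosis definition alone, so the numeric rule for local failure does not protect it.

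**Working it through.** **1. Whom the stated reasons cover.**

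| Step | Where | Stated reason to know the arm |
|---|---|---|
| Planning and treatment-time calculation | 8.2 | Yes |
| Data processing and plan checks | 8.2 | Yes |
| Radionecrosis call (radiologist / board) | 8.1.1 | None given |
| Local failure measurement | 8.1.1, no reader named | None given |
| Three-monthly MRI read | Table 1, 8.3.9, no reader named | None given |

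The coding and access rules in 12.1 protect confidentiality and do not mask a reader. No section provides a masked, central or independent read. The figure in 8.2 and the flow chart in 8.3 were not available for this check; the text around them gives no sign that they deal with masking.

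**2. Which calls can move the endpoint.** Growth of 20% or more from nadir is local failure by rule. Confusing failure with radionecrosis leaves ALE status as it is. What remains is growth below or near 20%, where the call is event or no event.

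**3. Reproducing the plan's own figure.** Section 4.4 uses a two-sided pooled Z test evaluated exactly:

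Z = (x1/n - x2/n) / sqrt(p(1-p) x 2/n), with p = (x1+x2)/(2n); reject if |Z| >= 1.96. The rejection probability is the sum of Bin(x1; n, P1) x Bin(x2; n, P2) over the rejection region.

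With n = 59, P1 = 0.30 and P2 = 0.10, power is 0.8051. With both at 0.10, alpha is 0.0507. Both match 4.4.

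**4. Illustration of the stake.** Inputs: n = 130/2 = 65 per arm. There is no true difference. True ALE risk is 0.30 (the standard arm in 4.4) or 0.20 (the mean of 0.30 and 0.10). The recorded fSRT rate is lowered by d. The value of d is an assumption, as is its direction.

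| d | Patients (65 x d) | Two-sided error, risk 0.20 | Two-sided error, risk 0.30 |
|---|---|---|---|
| 0 | 0 | 0.049 | 0.052 |
| 0.01 | 0.65 | 0.051 | 0.054 |
| 0.02 | 1.3 | 0.058 | 0.059 |
| 0.03 | 1.95 | 0.070 | 0.069 |
| 0.05 | 3.25 | 0.11 | 0.10 |

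The part of this error that favours fSRT rises from 0.024-0.026 at d = 0 to 0.059-0.062 at d = 0.03.

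**5. How much misreading each row needs.** Share of all fSRT events not called = d / risk:
- 1 point: 0.01/0.20 = 5%, or 0.01/0.30 = 3.3%.
- 3 points: 0.03/0.20 = 15%, or 0.03/0.30 = 10%.
- 5 points: 0.05/0.20 = 25%, or 0.05/0.30 = 17%.

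Share of borderline fSRT calls not made = d / (risk x borderline share), with the borderline share also assumed:
- Share 0.5: 3 points needs 0.03/0.10 = 30% or 0.03/0.15 = 20%; 5 points needs 50% or 33%.
- Share 0.2: 3 points needs 0.03/0.04 = 75% or 0.03/0.06 = 50%; 5 points needs 125% (impossible) or 83%.

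**The case against.** The strongest reply is that the trial openly calls itself open label and takes its endpoint from routine follow-up scans. Using routine reads in a phase II trial is a disclosed pragmatic choice, and asking for a masked read is partly preference. That lowers the weight of the point. It does not remove it: 8.2 sets out to justify the absence of blinding, and its justification does not reach the endpoint read. Who reads a scan, and what they know at that moment, is trial conduct that belongs in the protocol and cannot be settled later in an analysis plan.

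The size of any bias is assumed throughout. One point is barely above nominal, and five points is impossible in one of the scenarios above. This objection stands in full.

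Three stronger readings are tempting, and the protocol does not support them.
- **That 8.2 forbids a masked read or contradicts 8.1.1.** It does neither; it is silent about the reader.
- **That the readers are known to be unmasked.** Open label makes it plausible, particularly for a multidisciplinary board, but no section says so.
- **That bias would run in favour of fSRT.** The Summary and 4.4 expect fewer events overall, but section 1 reports equivalent incidence in smaller metastases. The remark in 8.7 that with fractionation "there are fewer toxic effects on healthy cells" concerns toxicity, not local failure. Nothing shows that the reading radiologist shares the investigators' expectation.

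**Conclusion.** The point holds as a modest gap with a cheap remedy. The stated reasons for not blinding do not apply to the reading of the follow-up MRI, no section masks that read, and one component of the primary composite rests on judgement without a size cut-off. The exposure is confined to borderline growth being called an event or not.

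The numerical stake is illustrative only. It assumes no true difference, a risk of 20-30%, 65 analysed per arm and under-calling in the fSRT arm alone. On those terms, two patients not called (3 points) moves the two-sided error from about 5% to about 7%. The 10-11% figure is an upper case that needs 17-25% of all fSRT events to go uncalled. The protocol gives neither the borderline share nor any bias size, so this is no evidence that the trial's result will be biased. A later masked re-read of the scans could also still correct a problem.

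**What to change.** - **8.2:** limit the statement that blinding is impossible to patients and radiotherapy staff.
- **8.1.1:** state that the existing reader or readers of the follow-up MRI record size change, perfusion and the ALE call on the case report form before being given the arm or number of fractions, and note if the arm was already known.
- **Endpoint:** keep the definition as it stands (radiologist / multidisciplinary board). Moving to a single radiologist's call would change the endpoint more than this gap requires.
- **Patient care:** treatment information is available once the call is recorded.
- **Analysis:** keep the intention-to-treat comparison as primary, and add a sensitivity analysis that flags or excludes calls made with the arm known.

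Section 8.1.1 names a reader for radionecrosis only. The new text should therefore say who makes the local failure call, and not assume that it is the same radiologist.

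The cost is a protocol amendment and a small change to the case report form and the MRI request. No scans are added, and no readers if the existing ones are used. Masking will be incomplete where local readers can see the treatment record, which is why the flag is needed. Scans read before the change cannot be covered prospectively; only a masked re-read, with its extra reading time, would reach them. The change does not supply a size or perfusion cut-off for radionecrosis, which is a separate matter.
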